prospective fashion at three antenatal clinics. Our most complete data to date is from Jawi Health Centre in Amhara Region during the 2018 peak transmission season. In this study population, 28 of 34 pregnant women (mean age 24.2 years) who presented to the antenatal clinic were asymptomatic, 26 of 34 were in the first trimester, and 13 of 34 were primigravida. Malaria positivity amongst asymptomatic women was 3/34 (8.8%) by microscopy, 1/34 (2.9%) by RDT, 12/34 (35.3%) by commercial LAMP, and 12/34 (35.3%) by ELUCIDx, and 11/34 (32.3%) by qPCR. The sensitivity of microscopy in pregnant women in this study population was 25.0% (95% CI 5.49 - 57.19%), RDT 8.33% (0.21 - 38.48)), commercial LAMP 81.82% (48.22 - 97.72), ELUCIDx 100.00% (73.54 -100.00) and qPCR 91.67% (61.52 - 99.79) using a consensus gold standard. These data suggest that ultrasensitive diagnostics like LAMP are able to detect malaria far more frequently than traditional diagnostic methods when coupled to active case detection of symptomatic and asymptomatic pregnant women. The marked decrease in sensitivity for microscopy and RDT in phase 2 as compared to phase 1 is directly linked to the low level of infection found in asymptomatic pregnant women. We predict that greater detection of malaria in pregnancy with LAMP-based active case detection will lead to better critical outcomes such as LBW in pregnancy in the full-scale LAMPREG trial.

Table 3: Performance of LAMP compared to microscopy and rapid diagnostic tests (RDT) in asymptomatic and symptomatic pregnant women (N=34, Jawi, Amhara Region), phase 2 proof of concept prospective study with active case detection.

Method	Sensitivity % (95%CI)	Specificity % (95%CI)
Microscopy	25.00 (5.49 - 57.19)	100.00(84.56 - 100.00)
RDT	8.33 (0.21 - 38.48)	100.00(84.56 - 100.00)
Meridian LAMP (competitor)	81.82 (48.22 - 97.72)	86.96 (66.41 - 97.22)
ELUCIDx LAMP	100.00(73.54 -100.00)	100.00 (84.56 - 100.00)
qPCR	91.67 (61.52 - 99.79)	100.00 (84.56 - 100.00)

In additional preliminary data from Gojeb, Southwest Ethiopia, our study team has shown that treating pregnant women positive by LAMP has benefits in terms of fetal hemoglobin and birth weight, with the former reaching statistical significance (n=200, p<0.05). This is important data which requires confirmation in a full-scale trial across several epidemiological settings in Ethiopia.

Outcome			p Value
measure	LAMP Arm Mean (n=150)	SOC Arm Mean (n=50)	(t test)
Birth Weight (g)	3059	2965	0.1478

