symptomatic and asymptomatic first and second trimester mothers will be included in the study and individually randomized to one of two arms: standard of care or enhanced cased detection arms using LAMP for malaria. Mothers will be enrolled during a twelve-months period from October 2020 to October 2021 and then followed until 28 days after delivery. Given the rate of pregnant mothers at the locations, we anticipate that the required minimum of 2583 mothers will be enrolled in the study during the study period. In the first standard of care arm, venous blood sample will be collected from each study participant and the presence of *Plasmodium* infection will be diagnosed by microscopy in symptomatic patients. Pregnant women who test positive for malaria will be referred and treated for malaria with quinine or ACTs as per national guidelines. In the second (test) arm, mothers whether symptomatic or asymptomatic will be tested by a commercially available CE-approved LAMP malaria test (Meridien Biosciences, Illumigene Malaria M kit, Cincinatti, USA) and Human Diagnostics LoopAMP (Wiesbaden, Germany) at each clinic visit in addition to RDT/microscopy. The commercial LAMP tests can distinguish P. falciparum and P. vivax and treatment will be given according to national guidelines. The purpose of doing all tests in the intervention arm is to determine how many additional cases LAMP identified. The primary outcome is the proportion of deliveries with low birth weight, with secondary outcomes of: (i) absolute birth weight; (ii) maternal hemoglobin; (ii) neonatal hemoglobin at birth (Standard Hgb testing from peripheral blood or finger prick); (iv) neonatal mortality; (v) stillbirth; and (vi) prematurity in each of the two arms. Additionally, signs of current or past *Plasmodium* sequestration in the placenta will be evaluated.

[figure not shown]

Figure 1: Flowchart summarizing randomized trial

There will be a total of at least five antenatal visits (mandatory). Emergencies (medical consultation outside the planned visit) will be recorded for each included woman. Visit 1 and 2 may be combined for mothers who present in the second trimester. The following table summarizes the procedures to be conducted at each visit.

Visit #	Time frame	Aim	Action for the study
1	Visit at health care center	Inclusion	Enrolment and randomisation
2	26 weeks gestation	Follow up	Malaria testing as per inclusion arm (2mL venous blood on EDTA) +ANC regular care Maternal Hgb

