3	32 weeks gestation	Follow up	Malaria testing as per inclusion arm (2mL venous blood on EDTA) +ANC regular care Maternal Hgb
4	36-38 weeks gestation	Follow up	Malaria testing as per inclusion arm (2mL venous blood on EDTA) +ANC regular care Maternal Hgb
5	Delivery	Delivery visit	Foetal Hb Maternal Hb Malaria testing Birth weight + size Weeks of pregnancy - preterm? Placenta blood Death
6	28 days after birth	Néonatal assessment visit	Newborn weight/ hemoglobin/ death/ other

Table 5: Actions to be taken at each visit to the health center by a pregnant mother

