5.7.2. Blood sample collection and processing

For microscopy, two milliliters of venous blood will be collected from each study participant using EDTA anticoagulant test tube. Soon after venous blood collection, a drop of blood will be taken for RDT test and another two separate drops of blood will be placed on frosted microscope slides to prepare thin and thick blood films. For LAMP, two milliliters of venous blood will be collected from each study participant using EDTA anticoagulant test tube. LAMP will be performed at the respective health centers based on the manufacturer's recommendation (Meridian Diagnostics, and Human Diagnostics). Dried blood spot (DBS) samples will also be collected from all individuals by using two drops of blood placed on a Whatmann filter paper. DBS will be stored in AHRI for further testing if required. DBS will also be sent to the University of Calgary, Canada (cf MTA) for ultrasensitive malaria technique (qRT PCR) and parasitic whole genome sequencing. For placental infection assessment, placental blood will be collected on anticoagulant after delivery.

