Secondary outcomes were signs of placental malaria infection at delivery, defined as a composite of maternal malaria (detection of infection in peripheral blood with post hoc gold standard testing) or placental malaria (detection of infection in placental blood with microscopy, molecular testing for active infection, or malaria pigment in blood smear monocytes for signs of past infection)

Secondary outcomes include maternal anemia (any: hemoglobin level <11 g/dL; moderate: hemoglobin level <9 g/dL) during each ANC visit and at delivery. We will use the categories "no anemia", "mild anemia", "moderate anemia" and "severe anemia" using the reference values for each pregnancy trimester. Values will be disaggregated according to gestational age.

Secondary outcomes during pregnancy comprised maternal malaria, detected with any method and by each method separately. This outcome was further stratified by patent infection (positive microscopy or malaria rapid diagnostic test) and sub-patent infection (negative microscopy and malaria rapid diagnostic test and positive LAMP–PCR). Morbidity outcomes assessed during pregnancy comprised clinical malaria (documented or history of fever plus positive malaria rapid diagnostic test or microscopy) and unscheduled clinic visits for any reason and for all reasons unrelated to malaria.

2. Analysis methods

Mean values of quantitative variables will be compared using a two-sided t-test with a significance of p < 0.05. We will use a negative binomial model to assess the effect of asymptomatic malaria screening using the number of (i) both microscopic and submicroscopic and (ii) submicroscopic *P. falciparum* infections occurring during pregnancy with an adjustment for the confounding variables. Multiple test correction will be implemented.

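### The SAP's patent and sub-patent infection outcomes rest on films and RDTs that Protocol 5.2 provides differently by arm, so comparing arms on them can be biased in either direction

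*SAP*

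**What the plan says.** SAP Section 6.1 (Outcome definition) stratifies the secondary outcome of maternal malaria into "patent infection (positive microscopy or malaria rapid diagnostic test) and sub-patent infection (negative microscopy and malaria rapid diagnostic test", with sub-patent infection also needing a positive LAMP-PCR result. It does not limit the split to one arm and gives no score for a visit without a film or RDT. SAP Section 6.3 says that outcomes will not be imputed.

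Protocol 5.2 sets testing by arm. In standard of care, "infection will be diagnosed by microscopy in symptomatic patients", and no RDT is named. Intervention women, with or without symptoms, have LAMP "at each clinic visit in addition to RDT/microscopy". Table 5 describes visits 2 to 4 as "Malaria testing as per inclusion arm"; the delivery visit lists malaria testing with no reference to arm.

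Protocol 5.7.2 reads differently: "For microscopy, two milliliters of venous blood will be collected from each study participant using EDTA anticoagulant test tube". It goes on: "Soon after venous blood collection, a drop of blood will be taken for RDT test", and then describes thick and thin films, with no limit by arm or symptoms. It also states: "Dried blood spot (DBS) samples will also be collected from all individuals". Some of these spots go to qRT-PCR.

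**The concern.** Both outcomes are built from test results, and on the Protocol 5.2 reading the amount of conventional testing is part of the randomised intervention. An asymptomatic control woman then has neither a positive film or RDT, which patent infection needs, nor the negative film and RDT that sub-patent infection needs. The problem does not depend on LAMP being run in one arm only; it would remain if LAMP were dropped from the definitions.

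An arm comparison of infections is in view. SAP Section 6.2 plans a negative binomial model of the number of microscopic and submicroscopic infections to assess the effect of asymptomatic screening. If infections are counted from film, RDT and LAMP results, the count rises with the number of tests. Unless the SAP says how untested visits are scored, the analyst's coding choice can decide the result. Clinical malaria, defined by fever plus a positive RDT or film, has a milder form of the problem if only one arm has RDTs.

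**Working it through.** The plan gives no figure for women who cannot be scored, so the size is built from its other numbers.

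**Inputs**
- Total enrolment is 2583 (Protocol 5.6, SAP Section 3.3). This reproduces at 3:1 with 17.3% v 12.3%, two-sided 5%, 80% power and continuity correction: 538 controls, 4 x 538 = 2152, and 2152 x 1.2 = 2582.4, rounded up to 2583.
- The control share is 1/4 under the 3:1 ratio in the sample-size text and 1/3 under the 2:1 split in SAP Section 3.2. Both are shown because the SAP contains both.
- Asymptomatic share (Protocol 3): "28 of 34 pregnant women (mean age 24.2 years) who presented to the antenatal clinic were asymptomatic". That is 82.4%, exact 95% CI 65.5% to 93.2%.
- Film positivity is 3/34 = 8.8% (Protocol 3). The text attributes this to asymptomatic women but divides by all 34.
- Film positivity in symptomatic women is about 10/87 = 11.5%, derived from Protocol Tables 1 and 2: 10 PCR-positive of 87, sensitivity 90%, specificity 98.7%, so 0.90 x 10 + 0.013 x 77 = 10.0.

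**Share of the trial with no film or RDT at one visit (Protocol 5.2 reading)** = control share x asymptomatic share

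| Allocation | Controls | Untested at one visit | Share of trial | Over pilot CI |
|---|---|---|---|---|
| 3:1 | 2583/4 = 646 | 646 x 28/34 = 532 | 20.6% | 16.4% to 23.3% |
| 2:1 | 2583/3 = 861 | 861 x 28/34 = 709 | 27.5% | 21.8% to 31.1% |

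This is a single-visit figure. If visits were independent, the share of the trial made up of controls with no symptoms at any of four visits would be 0.25 x (28/34)^4 = 11.5% at 3:1, or 15.3% at 2:1. In the other direction, if control women have no RDT at all, sub-patent status fails for the whole control arm, 25% to 33% of the trial.

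**Apparent ratio for patent infection at one visit, no true difference.** Let s be positivity in symptomatic women, a positivity in asymptomatic women, and 6/34 the symptomatic share. Films alone are used in both arms, so any extra RDT yield in the intervention arm is ignored.
- Intervention shows (6/34)s + (28/34)a.
- Control shows (6/34)s if untested is negative, or s if untested is missing.

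| s | a | Intervention | Control, untested = negative | Ratio | Control, tested only | Ratio |
|---|---|---|---|---|---|---|
| 8.8% | 8.8% | 8.8% | 1.6% | 5.7 | 8.8% | 1.00 |
| 11.5% | 8.8% | 9.3% | 2.0% | 4.6 | 11.5% | 0.81 |

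These are illustrations, not bounds. With s = 11.5% and an assumed a = 3.0%, the two ratios are 2.2 and 0.39. If all three pilot film-positives were in the six symptomatic women, which the text does not settle, they are 1.0 and 0.18.

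**The case against.** The strongest objection is that the premise is unsettled. Protocol 5.7.2 can be read as films and RDT for every participant, and the absence of a control RDT is inferred from silence in 5.2. Objective 1 (Protocol 4.2) and the Gojeb pilot (Table 4) both describe the comparator as microscopy/RDT. The SAP also cites protocol v1.5, while the protocol reviewed is v1.1, so the testing rule may have changed. This stands as a reason not to state as fact that asymptomatic controls go untested. It does not remove the point, because 5.7.2 uses the same each-participant wording for the LAMP sample, although LAMP is an intervention-arm test. That wording therefore cannot be taken to override the arm definitions. Protocol 5.2 also separates drawing blood from every control woman from using microscopy in symptomatic ones.

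A reader might infer that screening will necessarily appear to raise patent infection. The documents do not support this. It needs untested visits to be scored negative, which the SAP nowhere says; the no-imputation rule points rather to missing, where the illustrated ratio is 0.8 to 1.0. A reader might also take a fifth of the trial as a floor. It is a one-visit estimate from 34 women at one site in peak season, and the interval reaches 16%.

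It is also fair that SAP Section 6.2 names no arm contrast of patent infection as such, and that SAP Section 5.5 allows submicroscopic infection to be identified by post hoc RT-qPCR. Overall infection could therefore be compared between arms by PCR. That supports the remedy, but Section 6.1 does not make it the rule.

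**Conclusion.** As written, a comparison of arms on patent or sub-patent infection is exposed to detection bias. On the Protocol 5.2 reading, about 21% (3:1) to 27% (2:1) of the trial would have no film or RDT at a given visit, 16% to 31% over the pilot interval and both allocations, and sub-patent status may be unscorable for every control woman. Under the pilot-based positivity assumptions, a true null would appear as a ratio of about 4.6 to 5.7 if untested means negative. If untested means missing, it would appear as about 0.8 to 1.0, and the control side is then only its symptomatic women, so the randomised comparison is lost. The direction depends on a coding rule the SAP does not state.

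If reconciliation shows that both arms have films and RDTs at every visit, the bias from conventional testing disappears and only the wording needs correcting. These are secondary outcomes. Low birth weight does not depend on these tests, so the primary comparison is unaffected. The change should be made but does not threaten the trial's main conclusion.

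**What to change.** 1. Reconcile Protocol 5.2, Table 5 and 5.7.2 in the current protocol version, so that it is clear who has a film and an RDT at each visit, by arm.
2. In SAP Sections 6.1 and 6.2, base any comparison of infection between arms on qRT-PCR of the dried blood spots, using only visits at which spots are taken in both arms. Confirm that schedule: neither Protocol 5.7.2 nor Table 5 gives one.
3. Keep the film/RDT/LAMP patent and sub-patent split as a description of the intervention arm only, as Protocol 5.8 already does for LAMP against microscopy.
4. State that untested visits are not scored as negative.
5. A split by PCR density is optional. If used, its cut must be stated in advance: Protocol 1.2 gives both about 50 parasites/µL (experienced microscopy) and 100 parasites/µL (below which films and RDTs are unreliable).
6. If it is confirmed that control women have no RDT, define clinical malaria for the arm comparison as fever plus positive microscopy in both arms.

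The cost is mainly SAP wording, plus the protocol clarification. The downside is timing: the arm comparison of infection waits for the post-trial PCR results, which SAP Section 3.6 schedules separately from the clinical analysis. Any density cut would only approximate film positivity.

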5.7.4. Loop-mediated isothermal amplification (LAMP)
5.8. Statistical Analysis Plan20
5.9. Data analysis and interpretation
5.10. Benefits and beneficiaries of the proposed study22
5.11. Dissemination of findings
5.12. Ethical Considerations
6.0. WORK PLAN
7.0 English Version of Questionnaire2
8.0 References

SUMMARY

Background: Malaria is one of the major public health problems in sub-Saharan Africa. It contributes significantly to maternal and fetal morbidity and mortality in affected countries.

Objective: The aim of this study is to evaluate the impact of enhanced case detection using molecular testing (LAMP) on maternal and infant morbidity and mortality in a prospective study design.

Method: A pragmatic randomized control diagnostic trial will be conducted from October 2020 until October 2021 in pregnant mothers at sites in Ethiopia. Both symptomatic and asymptomatic first and early second trimester pregnant women will be included in the study and individually randomized to either standard of care or enhanced cased detection arms using LAMP for malaria. Women (n=2583) will be enrolled during a twelve-months period encompassing the peak transmission seasons and then followed until delivery. In the standard of care arm, venous blood sample will be collected from each study participant and the presence of *Plasmodium* infection will be diagnosed by microscopy in symptomatic patients. Pregnant women who test positive for malaria will be referred and treated for malaria with quinine or artemisinin combination therapies (ACTs) as per national guidelines. In the intervention arm, mothers who are symptomatic or asymptomatic will be tested by a commercially available CE-approved LAMP malaria test and microscopy/RDT for malaria at each clinic visit and treated if positive by any test. Pregnant mothers who require treatment will be referred and treated with either quinine or artemisinin combination therapy (ACTs) as per national guidelines. The primary outcome is the proportion of deliveries with low birth weight based on WHO definition, with secondary outcomes of:(i)absolute birth weight; (ii) maternal hemoglobin;(ii) neonatal hemoglobin at birth;(iv) neonatal mortality; (v) stillbirth; and (vi) prematurity in each arm of the study.

Result Dissemination plan: The results of this study will be presented at national and international scientific conferences. It will also be published in a reputable journal.

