4.2. Specific objectives

- 1. To evaluate the impact of LAMP versus microscopy/RDT for the detection of malaria in pregnant mothers in terms maternal and infant morbidity and mortality.
- 2. To evaluate the impact of enhanced case detection of malaria in pregnancy by screening asymptomatic mothers at each antenatal visit until delivery.
- 3. To determine the impact of treating LAMP-positive asymptomatic and symptomatic pregnant women as compared to standard of care. Treatment is per national guidelines.

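### The SAP's clinical malaria outcome counts a positive RDT and recalled fever, which on the protocol's arm descriptions can add events only in the intervention arm; the size is uncertain and the outcome is secondary

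*SAP*

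**What the plan says.** SAP Section 6.1, in the text on secondary outcomes during pregnancy, lists "clinical malaria (documented or history of fever plus positive malaria rapid diagnostic test or microscopy". No recall window is given for the history of fever, and LAMP is not part of the definition.

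The protocol describes different testing by arm:

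- **Standard care (5.2):** "infection will be diagnosed by microscopy in symptomatic patients". RDT is not named.
- **Intervention (Summary):** women with or without symptoms are "tested by a commercially available CE-approved LAMP malaria test and microscopy/RDT for malaria at each clinic visit and treated if positive by any test". Section 5.2 says LAMP is done "at each clinic visit in addition to RDT/microscopy" and adds: "The purpose of doing all tests in the intervention arm is to determine how many additional cases LAMP identified".
- **Antenatal follow-up visits (Table 5):** "Malaria testing as per inclusion arm".

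Other text is less clear about standard care:

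- **Objective 1 (4.2):** "To evaluate the impact of LAMP versus microscopy/RDT for the detection of malaria in pregnant mothers".
- **Table 4 caption (Section 3):** the pilot control arm is described as microscopy/RDT.
- **Section 5.7.2:** "a drop of blood will be taken for RDT test and another two separate drops of blood will be placed on frosted microscope slides", with no arm restriction.

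The SAP states that it was written on protocol version 1.5. The protocol supplied is marked version 1.1.

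**The concern.** Because LAMP is left out, the definition looks as if it measures both arms alike. On the arm descriptions it does not, for two reasons.

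1. **RDT.** A febrile woman who is RDT positive and microscopy negative is an event in the intervention arm. In standard care she has no RDT and cannot be one.
2. **Recalled fever.** An intervention woman with no symptoms on the day is still tested, so an earlier fever plus a positive result makes her an event. A standard-care woman who is not classed as symptomatic is not tested. The inclusion questionnaire asks about symptoms and axillary temperature and has no separate question on past fever.

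Neither route can add an event in standard care alone, so the bias runs against the intervention. A true fall in symptomatic malaria could be hidden, or screening could appear to raise it. The SAP has no rule for equal ascertainment of this outcome.

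**Working it through.** The documents give no expected rate for clinical malaria, so there is no planned figure to reproduce for it. The usable inputs are the pilot accuracy data in Protocol Section 3.

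**1. Check the inputs.** Table 1 (87 symptomatic women) sums to 3+5+1+1 = 10 PCR-positive and 20+41+13+3 = 77 PCR-negative. Table 2 then reproduces:

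- Microscopy: 9/10 = 90% sensitivity, 76/77 = 98.7% specificity.
- RDT: 7/10 = 70% sensitivity, 75/77 = 97.4% specificity.

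**2. RDT route at phase 1 values.** Assume the same infection rate among febrile women in both arms. The ratio is P(microscopy or RDT positive) / P(microscopy positive). The overlap of the two tests' errors is not given, so the possible range is shown per 87 febrile women.

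| Rule | True positives | False positives | Total | Ratio |
|---|---|---|---|---|
| Microscopy alone | 9 | 1 | 10 | 1.00 |
| Either test, full overlap | 9 | 2 | 11 | 1.10 |
| Either test, independent errors | 10×(1−0.1×0.3) = 9.70 | 77×(1−76/77×75/77) = 2.97 | 12.67 | 1.27 |
| Either test, minimum overlap | 10 | 3 | 13 | 1.30 |

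Much of the excess is false-positive RDTs, which the outcome would still count. On true positives alone the ratios are 9/9 = 1.00, 9.7/9 = 1.08 and 10/9 = 1.11.

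**3. Other inputs.** Keeping phase 1 accuracy and assuming other infection rates p among febrile women:

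- Microscopy positive: 0.90p + (1−p)/77.
- Either test, full overlap: 0.90p + (1−p)×2/77.
- Either test, independent errors: 0.97p + (1−p)×(1−76/77×75/77).

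| Assumed infection rate | Full overlap | Independent errors |
|---|---|---|
| 5% | 1.22 | 1.49 |
| 20% | 1.05 | 1.18 |
| 30% | 1.03 | 1.14 |
| 50% | 1.01 | 1.10 |

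At phase 2 accuracy (Table 3: microscopy 3/12, RDT 1/12, both 100% specific):

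- Full overlap: 3/3 = 1.00.
- Independent errors: (1−0.75×11/12)/0.25 = 0.3125/0.25 = 1.25.
- Minimum overlap: 4/3 = 1.33.

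Phase 2 women were mostly asymptomatic (28 of 34), so these figures are only a rough guide to febrile women.

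**4. Recalled-fever route.** The ratio is 1 + (a×q×h)/(s×m), where

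- a and s are the shares of visits without and with symptoms;
- q is film positivity in women without symptoms;
- h is the share of those film-positive women who recall a fever;
- m is film positivity in symptomatic women.

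The documents do not give h. Take a = 28/34, s = 6/34 and q = 3/34 (Jawi), m = 10/87 (Gondar), and treat every symptomatic woman as febrile. The ratio is then 1 + (0.0727h)/(0.0203) = 1 + 3.58h: 1.00 at h = 0 and 1.36 at an assumed h of 10%. These inputs mix two sites. The 34 behind q also includes the six symptomatic women, although the protocol labels the rate as asymptomatic. Only the direction is used below.

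**5. What the RDT route could hide.** If it multiplies the risk ratio by 1.10 to 1.27, a true ratio of 1/1.10 = 0.91 to 1/1.27 = 0.79 would read as 1.00. That is a true reduction of about 9% to 21%.

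**6. Same rule in both arms.** With fever at the visit plus microscopy in both arms, the numerator and denominator of the ratio in step 2 are the same quantity, so the no-effect ratio is 1.00.

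**The case against.** The strongest reply is that absence of RDT in standard care is not established. Objective 1 and the Table 4 caption both describe the comparator as microscopy/RDT, and 5.7.2 describes an RDT drop without naming an arm. If symptomatic standard-care women do have RDT, the RDT route largely disappears. This stands as a condition on the point, but it does not dispose of it. Section 5.7.2 also describes LAMP blood from every participant, so it cannot settle which arm gets which test, and the recalled-fever route would remain. The version difference adds to the doubt, because standard-care testing under version 1.5 cannot be seen.

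Second, the outcome already requires fever, which is on the questionnaire's symptom list. A currently febrile standard-care woman would therefore get microscopy. A reader might infer that testing only symptomatic women is the main source of bias. It matters only for recalled fever in women not classed as symptomatic, and that term is not defined. Such a woman might be classed as symptomatic and tested. Follow-up forms are not in the supplied documents.

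Third, a reader might take 10% as a minimum, or 10% to 27% as the expected bias. The documents support neither. The range rests on 10 PCR-positive women (exact 95% intervals 56% to 100% for microscopy sensitivity, 35% to 93% for RDT), one infection rate and an assumed overlap. Phase 2 accuracy allows no bias at all. Nor is 33% a ceiling: an assumed 5% infection rate at phase 1 accuracy gives up to 1.49 with independent errors.

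Finally, a reader might infer that this is the trial's main maternal morbidity outcome. No document says so. It is not among the protocol's outcomes, the SAP primary objective names maternal anemia, and SAP Section 6.2 assigns no test to clinical malaria by name.

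**Conclusion.** The point holds in a conditional form, for a secondary outcome. On the arm descriptions in the supplied protocol, the SAP definition can add clinical malaria events only in the intervention arm, so under no true effect it reads equal or higher there. For the RDT route, 1.10 to 1.27 is an illustration at phase 1 values, within 1.00 to 1.33 across the two pilot data sets; the figure moves with the infection rate among febrile women and with error overlap. For recalled fever, the direction follows from the text but the size is unknown.

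This assumes that the outcome will be compared between arms, that true infection and fever rates are equal, that the slash in RDT/microscopy means both tests in the intervention arm (as the all-tests sentence in 5.2 indicates), and that standard care follows the Summary and 5.2. If standard care includes RDT for symptomatic women, only the recalled-fever route is left. The low-birth-weight primary outcome does not depend on any of this.

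**What to change.** 1. Reconcile the Protocol Summary, the Table 4 caption, Objective 1, 5.2 and 5.7.2 on which tests are used to ascertain outcomes in each arm, and check the result against the protocol version the SAP cites.
2. In SAP Section 6.1, define the between-arm clinical malaria outcome on what both arms receive: fever recorded at the visit (symptom form or axillary temperature above 37.5 °C) plus positive microscopy. Confirm that fever is recorded the same way at every visit in both arms.
3. Report RDT-only and recalled-fever cases descriptively, outside the between-arm comparison.
4. As a sensitivity analysis, use fever plus the already planned qRT-PCR on stored dried blood spots. Section 5.7.2 says spots are collected from all individuals but not at which visits, so confirm that both arms are covered at the same visits. This result must wait for the later laboratory testing.

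This changes outcome measurement only, not care, and should be settled before any comparison by arm. The cost is a short SAP edit and somewhat fewer counted events. On phase 1 counts, 1 of 11 to 3 of 13 either-test positives would leave the intervention-arm count, part of them false positives, along with any recalled-fever cases.
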